3.3.1. Experimental group (virtual reality)

The rehabilitation team (comprising a physician, speech therapist, physiotherapist, and psychologist) will establish an individualized rehabilitation protocol for the recovery of sensorimotor and proprioceptive function in the upper limb. This protocol will involve exergaming exercises with virtual reality, totaling 50 minutes, conducted three days a week for four consecutive weeks. The rehabilitation protocol utilizing virtual reality will be carried out using the VRRS Khymeia system. This system will include exercises in semi-immersive virtual reality (utilizing the VRRS HandBox,

an advanced upper limb skeleton tracking device) and immersive virtual reality exercises (created with a Head Mounted Display device).

Rehabilitation sessions will take place at the Department of Rehabilitation Medicine and Neurorehabilitation at the IRCCS Institute of Neurological Sciences in Bologna.

3.3.2. Control group

Patients in the control group will undergo rehabilitation treatment for sensorimotor and proprioceptive deficits in the upper limb according to standard clinical practice. They will have sessions three times a week, each lasting 50 minutes, for a duration of 4 weeks.

At the end of the 4-week treatment period, patients from both the treatment (VR) and control (C) groups will undergo post-test evaluations (T1).

3.3.3. Pre-Treatment assessment

- a) Motricity Index Test (Bohannon, 1999)
- b) Fugl-Meyer Test (Fugl-Meyer et al., 1975)
- c) Box and Block Test (Mathiowetz et al., 1985)
- d) Functional Indipendence Measure (FIM) (Beninato et al., 2006)
- e) Multidimensional Assessment of Interoceptive Awareness (MAIA) (Machorrinho et al., 2019)
- f) Thumb Location Test (Rand, 2018)
- g) Rubber Hand Illusion test (Romano et al., 2021)
- h) STIMA test (Tessari et al., 2015)
- i) Intelligence: Raven Progressive Matrices PM47 (Carlesimo et al., 1996);
- j) Executive functions: Trail Making Test, parte A (attenzione) e B (Giovagnoli et al., 1996);
- k) Memory: 15 words memory test (Ray, 1994), Corsi spatial short-term memory (Spinnler, 1987), digit span for verbal short-term memory digit (Orsini et al., 1987);
- Visuo-spatial ability: VOSP, Visual Object and Space Perception battery; shape detection and shape decision (Warrington & James, 1991)
- m) Attention: trial making test, matrici attentive, fluenza alternata.

3.3.4. Post-Treatment Assessment

- a) Motricity Index Test (Bohannon, 1999)
- b) Fugl-Meyer Test (Fugl-Meyer et al., 1975)
- c) Box and Block Test (Mathiowetz et al., 1985)
- d) Functional Indipendence Measure (FIM) (Beninato et al., 2006)
- e) Multidimensional Assessment of Interoceptive Awareness (MAIA) (Machorrinho et al., 2019)

- f) Thumb Location Test (Rand, 2018) NO
- g) Rubber Hand Illusion test (Romano et al., 2021)
- h) STIMA test (Tessari et al., 2015) NO
- i) Attention: trial making test, matrici attentive, fluenza alternata.
- j) Client Satisfaction Questionnaire-8

4. Outcome

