3.2. Population

Inclusion criteria:

- Age between 18 and 85 years;
- Female and male;
- Diagnosis of stroke outcomes occurring between 2 months and 18 months prior to enrollment;
- Impairment of upper limb functionality (Motricity Index with total score for the upper limb ≤ 80);
- Sensorimotor and proprioceptive impairment of the upper limb (Negative Thumb Location Test in 3 out of 4 trials);
- Signed informed consent to participate in the study.

Exclusion criteria:

• Ongoing clinical instability;

- Severe psychiatric comorbidity that may interfere with adherence to the proposed treatment protocol (e.g., severe personality disorders, severe psychomotor agitation);
- Severe impairments in upper limb motor function: Motricity Index Scale with the following cutoffs: pinch grip < 11, elbow flexion < 14, shoulder abduction < 14;
- Severe deficit in verbal comprehension: Token Test (Spinnler 1987) with a score < 2;
- Severe spatial neglect: Barrage Test (Albert 1973) score > 3.

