4.1. Primary endpoint

In order to assess the effect that the proposed treatment has on the sensorimotor and proprioceptive impairment of the upper limb, a comparison is conducted between the baseline assessments (T0) and those performed at the end of the 4-week rehabilitation treatment (T1).

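### The only test the protocol ties to proprioceptive impairment is marked NO at T1 without explanation, and no other T1 instrument is named for that part of the endpoints

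*Protocol*

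**What the plan says.** Protocol section 3.2 (Population) requires for entry "Sensorimotor and proprioceptive impairment of the upper limb (Negative Thumb Location Test in 3 out of 4 trials". No other test is linked to this impairment anywhere in the protocol.

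Section 3.3.3 (Pre-Treatment assessment) lists "f) Thumb Location Test" at T0 without restriction. Section 3.3.4 (Post-Treatment Assessment) keeps the same item letter but reads "Thumb Location Test (Rand, 2018) NO". The STIMA test, item h) of that list, carries the same mark. Neither mark is explained.

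Section 4.1 states the purpose of the primary endpoint as assessing "the effect that the proposed treatment has on the sensorimotor and proprioceptive impairment of the upper limb", by comparing T0 with T1. The first bullet of section 4.2 sets up the same comparison for VR against conventional rehabilitation. Section 5.2 analyses pre-test and post-test scores within the VR group, and T0 and T1 scores between the VR and C groups with the Mann-Whitney test. None of these three sections says which instrument carries the proprioceptive part.

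**The concern.** A comparison of T0 with T1 needs the same measure at both visits. The assessment list for T1 appears to leave out the one measure that the protocol itself uses to decide whether a patient has the impairment under study.

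Proprioception is not a side issue here. It appears in the hypotheses (1.1), the aims (1.2), the primary objective and the comparative secondary objective (2.1, 2.2), both efficacy endpoints (4.1, 4.2), and the case for clinical adoption (section 6). Section 5.2 also says that the pilot should estimate variation in the outcome measures for a possible larger trial. It could not do so for this test.

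No analysis plan can repair the gap later, because a T1 assessment that is not made cannot be recovered after the visit.

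**Working it through.** The protocol gives no effect size, standard deviation or power on this point, so there is no figure of its own to reproduce. The check is a comparison of sections followed by a count.

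**Sections side by side**

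| Section | Role | Thumb Location Test |
|---|---|---|
| 3.2 | Entry criterion | Negative in 3 of 4 trials |
| 3.3.3 | T0 list | Item f), no restriction |
| 3.3.4 | T1 list | Item f), marked NO |
| 4.1 | Primary endpoint, T0 against T1 | Not named; construct includes proprioception |
| 4.2 | VR against C, T0 and T1 | Not named; construct includes proprioception |
| 5.2 | Analysis of scores at both times | Not named |

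**What else remains at T1.** The unmarked items in 3.3.4 are the Motricity Index, Fugl-Meyer, Box and Block, FIM, MAIA, the Rubber Hand Illusion test, the attention tests and the satisfaction questionnaire. The protocol designates none of them as the proprioceptive measure and specifies no subscale of any of them. Among the instrument sources in the reference list, only the one cited for the Thumb Location Test has proprioception in its title.

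**Count of paired scores on this test.** Inputs from section 5.1: 20 patients, 10 per arm, 20% potential dropout. The protocol does not say whether 20 is before or after dropout; here dropout is taken off the 20.

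- Completers: 20 × (1 − 0.20) = 16; per arm, 10 × (1 − 0.20) = 8.
- If NO means not done: 0 pairs of 20 planned, and 0 of 16 completers.
- If the test is repeated: up to 20 pairs (10 per arm), or 16 (8 per arm) after dropout.

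**Consequence for the analyses in 5.2.** With no T1 score, the change within VR and the T1 comparison of VR with C are both undefined for this test. A T0 comparison between arms remains possible, but it says nothing about treatment.

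**A limit on the repeated test.** Every patient is selected for a poor score on this four-trial test. Some improvement from T0 to T1 would be expected from regression to the mean alone, if scores vary from one occasion to the next. The within-VR comparison in 5.2 cannot separate that from a treatment effect. The control arm is selected by the same rule, so the VR-versus-C comparison can.

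**The case against.** **The mark may be an editing remnant.** This is possible. It is unexplained, and both marked items keep their letters, whereas the intelligence, memory and visuo-spatial tests given only at T0 are absent from the T1 list altogether. Not done at T1 is the natural reading but not a certain one, so the count of 0 is conditional on it. The need to reconcile stands either way, because an assessor working from 3.3.4 could skip the test, and different assessors could act differently.

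**Proprioception may be captured by another T1 test.** A reader might infer from the mark that proprioception cannot be measured at T1 at all. The protocol does not support that. The Fugl-Meyer and Rubber Hand Illusion tests stay at T1 with no domain assigned, and the introduction links body representation and embodiment to proprioceptive signals. What stands is narrower: no T1 instrument is named for this purpose.

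**The test may be meant only for screening.** Sections 4.1 and 4.2 do not name it as an outcome, and other tests are given only at T0. That reading is tenable, but it leaves the proprioceptive endpoint with no instrument, which also has to be corrected.

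**This is a small pilot and the other scales remain analysable.** That is true, and it limits the damage to the proprioceptive part. It does not remove the conflict from the primary endpoint.

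**Conclusion.** The point holds as an internal contradiction. The only test the protocol ties to the impairment is marked NO at T1, while the primary endpoint and the comparative secondary endpoint call for T0 and T1 data on that impairment and name nothing else to supply the proprioceptive part. On the assumption that NO means not done, the loss on this test is complete: no paired score in either arm, where repetition would give about 16 to 20.

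A reader might also infer that every objective and endpoint is undermined. That goes too far: the satisfaction objective (2.2) and the satisfaction endpoint (4.2) do not depend on this test, and the motor and functional scales are still collected at both visits.

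The correction should be made before patients reach T1, since it reaches the primary endpoint and the missing scores could not be recovered afterwards.

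**What to change.** Reconcile section 3.3.4 with 4.1, 4.2 and 5.2. The preferred edit has three parts:

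1. Remove NO from item f) in 3.3.4, so that the Thumb Location Test is repeated at T1 in both arms.
2. Name it in 4.1 and 4.2 as the proprioceptive outcome.
3. State in 5.2 that the conclusion on proprioception rests on the VR-versus-C comparison, and that the within-VR change is descriptive because patients are selected for poor scores on this test.

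If the test will not be repeated, name another instrument given at both T0 and T1 as the proprioceptive measure. Failing that, drop the claim of proprioceptive recovery from the hypotheses, aims, objectives, endpoints and section 6. Deleting the word alone would not be enough, because 3.2 uses this one test for the sensorimotor and proprioceptive parts together. The protocol would then also have to say which scale carries the sensorimotor part.

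Clarify the NO beside the STIMA test in the same edit.

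The cost of the preferred edit is a few lines of text, submitted as an amendment if the protocol is already approved, and one short extra bedside test at T1 that assessors already give at T0. Section 7 says that the expertise to assess proprioception is available.

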4.1. Primary endpoint

In order to assess the effect that the proposed treatment has on the sensorimotor and proprioceptive impairment of the upper limb, a comparison is conducted between the baseline assessments (T0) and those performed at the end of the 4-week rehabilitation treatment (T1).

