1.2. Study aim

The primary aim of this study is to assess the effectiveness of a neurorehabilitation protocol using a virtual reality system for recovering sensorimotor and proprioceptive deficits in the upper limb of patients with post-stroke outcomes.

The secondary objective is to compare the outcomes, defined as the recovery of sensorimotor and proprioceptive function in the upper limb, between patients undergoing rehabilitation with virtual reality and those undergoing standard upper limb rehabilitation as per routine clinical practice.

2. Study objectives

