2.1. Primary abjective

Assessing the effect of a rehabilitation protocol using a virtual reality system for the recovery of sensorimotor and proprioceptive function in the upper limb in patients with stroke outcomes.

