2.2. Secondary objective

- Comparing the outcomes of a rehabilitation protocol using virtual reality against the standard rehabilitation protocol administered as per normal clinical practice for the recovery of sensorimotor and proprioceptive function in the upper limb in patients with stroke outcomes.
- Assessing the satisfaction of patients with stroke outcomes regarding the implementation of an upper limb rehabilitation program conducted with virtual reality.

3. Material and method

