3.1. Study design

Randomized control trial without pharmaceuticals use.

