4.2. Secondary endpoint

- To compare the effect of virtual reality rehabilitation for sensorimotor and proprioceptive deficits in the upper limb to conventional rehabilitation, a comparison is conducted between the assessments at T0 and T1 within the virtual reality treatment group (VR) and the group undergoing rehabilitation as per standard clinical practice (C).
- To assess patient satisfaction with the proposed experimental treatment, a validated questionnaire
 is administered to investigate patient satisfaction. The data are processed by calculating the mean,
 median, mode, and standard deviation for all 8 items. This approach allows for identifying the
 patient's overall considerations regarding the proposed treatment through a statistical summary
 that includes measures of central tendency (mean, median, mode) and data dispersion (standard
 deviation).

5. Data analysis

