5.2. Statistical analysis

The data analysis will be conducted using the Statistical Package for Social Science (SPSS version 26.0).

The preliminary data obtained from the pilot study will allow for estimating the variation in outcome measures between pre-test and post-test and between the treatment and control groups, providing insights for a potential subsequent trial with a larger sample.

The data will be analyzed based on the stated objectives, which include:

- Descriptive analysis of socio-demographic data for the experimental and control groups, including mean and standard deviation.
- The effect of the virtual reality rehabilitation protocol in the treated group will be assessed by comparing the scores of evaluation scales at pre-test and post-test. Data distribution will be tested using the Shapiro-Wilk test. The non-parametric Friedman test will be used in case of non-normal distribution, while ANOVA will be utilized in case of normal distribution. The significance level will be defined at $p \le 0.05$.
- The effect of the virtual reality rehabilitation protocol compared to the standard rehabilitation protocol will be assessed by comparing the scores of scales at T0 and T1 between the VR and C groups using the non-parametric Mann-Whitney test for independent samples.

6. Relevance

If the experimental hypotheses will be confirmed, the use of the virtual reality rehabilitation system could be implemented in routine clinical practice to rehabilitate sensorimotor integration in patients with stroke outcomes. An innovative approach employing virtual reality techniques aims not only to enhance patient treatment adherence but also to support proprioceptive and sensorimotor rehabilitation through the body illusion paradigm, which is not achievable in traditional rehabilitation. The enhancement of proprioceptive and sensorimotor aspects is considered crucial for the rehabilitation of neuromotor impairment. Therefore, by promptly implementing this type of intervention following a cerebrovascular event, one could hope for a faster and more effective functional recovery.

7. Feasibility

• The Rehabilitation Medicine and Neuro-rehabilitation Unit of the IRCCS Institute of Neurological Sciences in Bologna coordinates both the acute rehabilitation phase (with daily consultations at the Stroke Unit) and the sub-acute phase of the Stroke Clinical Pathway. Consequently, they daily admit patients with stroke outcomes at various stages of the

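### The primary result of this randomised trial is a before-after test within the VR arm alone; the VR-versus-control contrast, which is the one that isolates VR, ranks only as secondary

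*Protocol*

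**What the plan says.** Section 3.1 describes a "Randomized control trial without pharmaceuticals use". Section 5.1 plans 10 patients per arm, and section 3.3 gives both arms the same number, duration and weekly frequency of upper-limb sessions.

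The primary objective (section 2.1) names no comparator: "Assessing the effect of a rehabilitation protocol using a virtual reality system for the recovery of sensorimotor and proprioceptive function in the upper limb". In the primary endpoint (section 4.1), "a comparison is conducted between the baseline assessments (T0) and those performed at the end of the 4-week rehabilitation treatment (T1". Section 4.1 does not name the arm, but it speaks of the proposed treatment. Section 5.2 settles the matter: the effect of the VR protocol "in the treated group will be assessed by comparing the scores of evaluation scales at pre-test and post-test", by ANOVA or, if the data are not normal, by the Friedman test, at p ≤ 0.05.

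The randomised contrast ranks below this. Section 1.2 states: "The secondary objective is to compare the outcomes, defined as the recovery of sensorimotor and proprioceptive function in the upper limb", between VR and standard care. Section 2.2 repeats it as "Comparing the outcomes of a rehabilitation protocol using virtual reality against the standard rehabilitation protocol". Section 4.2 makes it a secondary endpoint, comparing T0 and T1 assessments "within the virtual reality treatment group (VR) and the group undergoing rehabilitation as per standard clinical practice (C", and section 5.2 assigns it a Mann-Whitney test.

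**The concern.** The control arm is matched on therapy time so that the type of therapy is what differs between the arms. The primary analysis does not use it, so half of the randomised patients contribute nothing to the primary result.

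A T0-T1 change in the VR arm contains, besides any effect of VR:

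- recovery over time, since section 3.2 admits "Diagnosis of stroke outcomes occurring between 2 months and 18 months prior to enrollment";
- other stroke rehabilitation, which section 3.3 lets patients receive alongside;
- retest effects on scales given twice about a month apart;
- regression to the mean on the Motricity Index, because entry requires a total of at most 80 and the scale is repeated at T1 (section 3.3.4).

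At stake is the answer to the question that section 1.2 puts first, the effectiveness of the VR protocol. A significant primary result would not show that VR contributed anything.

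**Working it through.** **No planned figure to reproduce.** Section 5.1 rests N = 20 on feasibility and pilot status and gives no effect size, SD or power. Only the dropout allowance can be used: 10 × (1 − 0.20) = 8 evaluable patients per arm.

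**Inputs from the protocol.** n = 10 per arm, or 8 after dropout (section 5.1); significance level 0.05 (section 5.2).

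**Assumptions.** The test is two-sided (the protocol does not say). The true VR-minus-control difference is zero. Both arms have the same mean change, d, in units of the SD of the change. The protocol gives no value for d, so a range is shown. Changes are normally distributed.

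**Step 1: the within-VR test under normality.** With one group and two time points, repeated-measures ANOVA is equivalent to the paired t-test. The probability of significance is P(|T| > t(0.975, n−1)), where T is noncentral t with n−1 degrees of freedom and noncentrality d√n. The critical values are 2.262 (n = 10) and 2.365 (n = 8). For example, at n = 10 and d = 0.5 the noncentrality is 0.5 × √10 = 1.581, which gives 0.293.

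| Shared change d | n = 10 | n = 8 |
|---|---|---|
| 0 | 5% | 5% |
| 0.25 | 11% | 9% |
| 0.5 | 29% | 23% |
| 0.8 | 62% | 50% |
| 1.0 | 80% | 68% |

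**Step 2: the planned alternative for non-normal data.** With two time points and no ties, Friedman's statistic is (2k − n)²/n on 1 df, where k is the number of patients who improve. At n = 10 it passes 3.84 only when k ≥ 9 or k ≤ 1. Each patient improves with probability Φ(d):

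- d = 0.5: Φ = 0.6915, and the test is significant with probability 14%.
- d = 1.0: Φ = 0.8413, probability 51%.

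At n = 8 (k ≥ 7 or k ≤ 1) the figures are 24% and 63%. At d = 0 the test's size is 2 × 11/1024 = 2.1% for n = 10 and 2 × 9/256 = 7.0% for n = 8. That difference in size is why the rates are higher at n = 8.

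**Step 3: the randomised contrast under the same assumptions.** In 20,000 simulated trials per setting, the exact Mann-Whitney test on T0-T1 change, VR against control, was significant in about 4% to 5% of trials at every d from 0 to 1.0. A change shared by both arms cancels.

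**Step 4: what the randomised contrast can deliver at this size.** For a two-sample t-test the noncentrality is δ√(n/2), with δ in SD of the analysed score.

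- 10 per arm: 80% power at δ = 1.33; 95% CI half-width 2.101 × √(2/10) = 0.94 SD.
- 8 per arm: 80% power at δ = 1.51; half-width 2.145 × √(2/8) = 1.07 SD.

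Adjustment for T0 would change the relevant SD to the residual SD, which the protocol does not give.

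**The case against.** **This is a pilot.** Section 5.1 says so, and section 5.2 says that the data will inform a possible larger trial. No rule in the protocol declares VR effective on the primary endpoint. This stands as a reason to ask for estimation and not for power. It does not rescue the uncontrolled contrast: section 5.2 also wants the variation between the treatment and control groups estimated, it attaches p ≤ 0.05 to the before-after test, and section 6 links confirmed hypotheses to possible routine use.

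**The controlled comparison is already planned.** It has an objective, an endpoint and a test, and section 9 commits to publication whatever the results. A reader might infer that the trial has no controlled evidence, or that non-specific improvement is bound to be reported as VR efficacy. The documents do not support either inference. The fault is one of rank.

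**Equal arms do not make a VR gain false.** The control is active rehabilitation, and section 1.1 separates being effective from being more effective than traditional care. If both treatments work equally well, part of the VR gain is a real treatment effect. This stands: a reader might take the 29%, 62% and 80% as false-claim rates, but they are so only if the shared change is wholly non-specific, which the protocol does not say.

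**Regression to the mean is limited.** It is tempting to add the failed Thumb Location Test as a second source, but section 3.3.4 marks that test NO at T1, so regression in its own score cannot enter the T0-T1 comparison. The Motricity Index argument remains, although the exclusion of low subscores (section 3.2) bounds selection from below as well. Recovery over time may also be small towards the 18-month end of the entry window.

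**Conclusion.** The point holds as a fault in the rank of the analyses. The primary result is an uncontrolled before-after test in the VR arm and cannot by itself support a claim that VR is effective, because nothing in it separates VR from the other sources of change.

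The direction is certain: any improvement shared by both arms raises the chance of a significant primary test and leaves the randomised contrast near its nominal 5% per test. The amount is not known. It runs from about 11% at a shared change of 0.25 SD to 80% at 1.0 SD with 10 patients, and is lower with Friedman at that size. These figures rest on an assumed shared change, a two-sided test and normal changes. They measure how readily the test becomes significant with no VR advantage over standard care; how much of that is error depends on how much of the change is non-specific.

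**What to change.** In sections 1.2, 2.1, 2.2, 4.1, 4.2 and 5.2:

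1. Make the VR-minus-control difference at T1, adjusted for the T0 score, the primary estimate.
2. Name one scale for it that is measured at both visits, for example the Fugl-Meyer. Without a single named scale, the 5% holds only test by test.
3. Report it with a 95% CI and call it a pilot estimate.
4. Report the T0-T1 change in each arm descriptively, with its CI, and attach no claim of effectiveness to it.

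**Cost.** Both arms already have T0 and T1 assessments, so no new patients, visits or measurements are needed. The price is that the primary question becomes comparative and the answer imprecise: 80% power only for differences of about 1.33 SD with 10 per arm, or about 1.5 SD with 8. The contrast should therefore not be presented as a powered test.
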